These equivalences indicate a criterion for resorting to more blood draws to offset recruitment failures. For example, if it appears that less than 100 subjects will complete the study, then resorting to 4 blood draws would provide compensation plus some bonus for the overall test. For HDL, the compensation would be "exact" (i.e., no bonus power) if the number of subjects had fallen to 96.

A decision to resort to 4 blood draws would have to take into account (1) the relative importance of the various outcome variables, (2) the relative importance of specific hypothesis tests, (3) design imbalances caused by recruitment failures. Based on the power computations given below, power appears to be in shortest supply for HDL. However, the benefit of four blood draws is most minimal for HDL. Therefore we anticipate that resorting to four blood draws will not be warranted.

Table 4
Roughly Equivalent Sampling Designs
(Under the Assumptions of the Working Model)

		Proposed Sampling Design	
Total Subjects	Blood Draws Per Subject	Total Subjects	Blood Draws Per Subject
96	4	100	3
94 94	4	100 100	3 3
92	4	100	3
92	4	100	3
91	4	100	3
88	4	100	3
	Sampli: Total Subjects 96 94 94 92 92 92 91	Bubjects Per Bubject 96 4 94 4 94 4 92 4 92 4 91 4	Sampling DesignsSamplingTotalBlood DrawsTotalSubjectsPer SubjectSubjects964100944100924100914100

The criterion used to establish rough equivalence of designs was the equality of the simple difference between averaged values:

 $V[(Y_{i,D,p}-\bar{Y}_{i,F,p'})] = (2/N)^*V[Z_{i,p}] + (2/NP)^*V[e_{i,d,p,t}]$

I. EFFECTS OF LABORATORY ASSAY MEASUREMENT ERROR

Under "additive errors" assumptions, laboratory measurement error is a sub-component of within-subject variance. Any unnecessary increase in within-subject variance reduces the power of the primary hypothesis tests. Therefore implementation of laboratory quality control procedures are crucial for the success of the study. Ideally, such procedures provide the scientist with instantaneous feedback so that gross errors are corrected. The data entry system will facilitate detection of gross errors by providing a simple algorithm for detection of extreme assay values.

A bias in a laboratory procedure that is consistent over time can, in theory, cancel out when the within-subject comparisons of the diets are computed. However the existence of such a bias is hardly reassuring as it could go hand-in-hand with other errors that do not cancel. Also one worries that the lab procedures might be partially "out of control".

Multi-laboratory studies add an additional source of concern. If the level of laboratory precision varies from one Field Center to another then the variance of the endpoint values will vary from Center to Center. This lack of constancy in variance will rob the collaborative analysis of a small amount of statistical power. It is possible to assume and model non-constant variance via the linear mixed model. However, this complicates the model and reduces degrees of freedom for testing hypotheses.

J. EFFECTS OF VARIATION IN NUTRIENTS

Measurement errors, variation of nutrients in raw food resources, and other cumulative effects result in inaccuracies in the preparation of experimental meals. As a result, some individuals receive more or receive less of certain nutrients than intended. This source of error can increase within-subject and between-subject variances. Inaccuracies that are consistent across time and diet can, in theory, cancel out when within-subject diet comparisons are made. However we should not trust that such cancellation will occur. In regard to minimizing food preparation errors or ameliorating their effects, we have five objectives:

1. Establish and refine food preparation procedures prior to data collection. Our pilot studies address this objective. In the metaphor of industrial quality assurance, this is analogous to building, tuning, and debugging production machinery so that resulting fabrications are "within tolerances" when production begins.

2. Minimize errors via quality assurance strategies. Appropriate strategies include foodpurchasing strategies, standard within-kitchen procedures for quality assurance, and assaying sample menus.

3. Estimate the mean and variance of the amounts of nutrients served to the study subjects. That is, at the end of the study we will provide information about the actual nutrient levels served. It is important to characterize the actual diets in any publications of the study.

4. Perform ancillary research to identify and evaluate sources of variation in food preparation. Identifying these sources of error will not only be important for present and future DELTA studies, but for other well-controlled feeding studies as well. In turn, these studies will enable us to advance the field of clinical nutrition research.

5. Evaluate "Portion Control". We will estimate variances in assayed nutrient levels in this study (Protocol 2) and compare them with variances obtained from the previous cross-over trial (Protocol 1). Compared with Protocol 1, Protocol 2 will make more extensive use of "portion control" food preparation methods. We hypothesize that variances will increase only slightly with this change.

K. DESIGN FOR SAMPLING THE PREPARED MENUS

A fractional-factorial design will be used to sample the meals fed to the study participants. The factors balanced in this design are period, cycle, center, diet and calorie level. ("Cycle" refers to the 8-day menu cycle that is repeated six times during the course of each feeding period.) there are 1,080 combinations of the levels of these factors: 3 periods x 6 cycles x 4 centers x 3 diets x 5 calorie levels. The fractional design includes only 24 of these 1,080 combinations.

The work load for each field center is best quantified in terms of menu cycles within feeding periods. Each such cycle comprises 24 meals: 3 meals/day on each of eight successive days, and each period comprises 6 cycles. During each period, each field center will send a total of two 8-day menu cycles to FALCC. For example, during cycle #1 of period #1, field

center "L" will contribute the sample menus for Diet D at calorie level #1. During this same cycle in period #1, field center "M" will contribute the sample meals for Diet D at calorie level #4. Later, center "M" contributes samples again during cycle #4 or period #1. The allocation of assignments to the field centers has been randomly chosen.

	Composite ID Number	Feeding Period	8-Day Menu Cycle	Field Center	Diet	Calorie Level	
-	1 2 3 4 5 6 7 8	1 1 1 1 1 1	1 2 3 4 4 5 6	LMPCLMPC	D D D E E F F F	1 4 2 5 3 3 1	
	9 10 11 12 13 14 15 16	2 2 2 2 2 2 2 2 2 2 2 2 2 2 2 2 2 2 2	1 2 3 4 5 5 6	C L M P C L M P	E F D D F F	4 1 1 5 3 2 5	
	17 18 19 20 21 22 23 24	3 3 3 3 3 3 3 3	1 2 3 4 5 6 6	P C L M P C L M	E F F D D E E	3 3 4 4 2 5	

Table 5Resulting Composites to be Assayed

The work load for FALCC for the monitoring of the diets includes: (1) preparation of the shipping kits for the 8 day diet samples, (2) receipt of frozen diet samples from Field Centers for a total of 192 menus, (3) preparation of 24 8-day composites, (4) assay of each of these composites for the appropriate nutrients, (5) archiving of the aliquots of each composite for possible future assay, (6) documentation of all assay QA/QC data, and (7) reporting of the assay results to the Coordinating Center.

The final statistical analysis will be based on 24 data values for each nutrient assayed. By comparison, Protocol 1 yielded 72 such data values. Thus, standard errors on estimates of mean levels in Protocol 2 will be roughly 73% larger than those obtained for Protocol 1. By design the sample of menu cycle composites should be representative of the meals actually fed to the study participants. However, because it is a sample rather than a census of the food served, some uncertainty will remain. If the sample size was any smaller this

uncertainty could become large enough to weaken the interpretability of the study. For the proposed design the half-width of confidence intervals for mean levels are as follows: Chol. ± 12.5 mg, TF% ± 0.49 %, MUFA% ± 0.19 %, SFA% ± 0.13 %, PUFA% ± 0.07 %.

Figures 9-13 provide information about the statistical power of the design for detecting departures from the targeted nutrient levels.

L. BALANCE OF THE FRACTIONAL FACTORIAL DESIGN

The frequency tables given below indicate degree of balance attained in this fractionfactorial design. For example, the first table shows that each center contributes samples for exactly two cycles during each period.

TADLE OF GENTER DI FERIOS						
	1	2	3	Total		
L	2	2	2	6		
С	2	. 2	2	6		
P	2	2	2	6		
M	2	2	2	6		
Total	8	8	8	t 24		

[figure not shown]
TABLE OF CENTER BY PERIOD

TABLE OF CENTER BY CYCLE

	1		2	3	4		5	6	Total
L		1	1	1		1	1	1	6
C	_	1	1	1		1	1	1	6
P		1	1	1		1	1	1	6
M		1	1	1		1	1	1	6
Total		4	4	4	1	4	4	4	24

TABLE OF CENTER BY DIET

	D		E		F	Total
L		2		2	2	6
C		2		2	2	6
Р		2		2	2	6
M		2		2	. 2	6
Total		8		8	8	24

Chapter 4 DELTA Protocol 2 5/05/94

TABLE OF CYCLE BY DIET

	D		E	F	Total
1		2	2	0	4
2		2	0	2	4
3		0	2	2	4
4		2	2	0	4
5		2	0	2	4
6		0	2	2	4
Total	1	8	8	8	r 24

TABLE OF CYCLE BY CALORIES

i	1	2	3	4	5	Total
1	1	0	1	2	0	4
2	1	1	1	1	0	4
3	2	1	0	1	0	4
4	0	0	1	1	2	4
5	0	2	2	0	0	4
6	1	1	0	0	2	4
Total	5	5	5	5	4	r 24

M. CONTINGENCY FOR IMPROVED STATISTICAL METHODS

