The longitudinal nature of the proposed cross-over design also admits the possibility of temporal and sequential effects. These include, for example, "period effects", "subject-by-period interaction", "subject-by-diet interaction", "carry-over effects", and miscellaneous interactions thereof. Subject-by-diet interaction (i.e., subject-to-subject variation in dietary responsiveness) is well established in animal studies and has been observed in some human studies. In the proposed study, subject-by-period and subject-by-diet interactions will be completely confounded. We anticipate that carry-over effects will not be in evidence -- partly because they are hard to detect and partly because of the length of the feeding periods. On the other hand, period effects are frequently noted in dietary feeding studies. When any of the above effects exist, formulation and use of model for the variance-covariance structure is particularly advantageous. When none of the above effects exists, inferences about differences between diets can be made using very simple computations. We anticipate that period effects and subject-bydiet interaction will be observed in the proposed study. These are easily handled and pose no If absent, the appropriate simple computations are just special cases of the major problems. proposed general algorithms.

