Table 1 gives an example of possible recruitment outcome. The centers will attempt to recruit roughly equal numbers of men and women. However, we anticipate that the proportion of males may turn out to be 60 to 75 percent. The recruitment of pre- and post-menopausal women is unconstrained (f + and f-, respectively.) In this chapter we will use "Black" to refer to African American subjects, and "White" to refer to all other subjects in the study. We anticipate that this later category may include a few Asian and Hispanic subjects. Chapter 5 gives details about population frames and recruitment goals for each of the Field Centers.

Table 1

Center	Gender	Black	White	Total
	F+	1	4	5
2	F -	2	4	6
-	M	6	8	14
	F+	3 2	3 3	6
L	F -	2	3	5
	M	7	7	14
	F+	2	4	6
M	F	1	4	5
	M	3	11	14
	F+	2	4	6
P	F -	1	4	5
	M	3	11	14
Total	F +	8	15	23
	F -	6	15	21
	M	19	37	56
		33	67	100
м:	Males			
F+:	Premeno	pausal F	emales	
F-:	Postmen	opausal	Females	
Black:	African	America	n subjec	ts
White:	Non - Af	rican Am	erican s	ubjects

Assumed Sample Design

D. RANDOMIZATION OF SUBJECTS TO TREATMENT GROUPS

At the end of the run-in period, remaining participants will be randomized to treatment groups (diet sequences) in such a way as to provide balance across the three diet periods. Highest priority will be given to balance within field centers to allow for clear interpretation of ancillary studies that will be performed. Balance within the demographic strata (across the field centers) will have next highest priority. Table 2 gives some indication of considerations of balance. Here "DEF", for example means Diet D followed by Diet E followed by Diet F.

		(Center		
	, c	L	M	P	Total
DEF	5	4	4	4	17
DFE	4	4	4	4	16
EDF	4	5	4	4	17
EFD	4	4	5	4	17
FDE	4	4	4	4	16
FED	4	4	4	5	17
Total	25	25	25	25	r 100

Table 2Proposed Allocation of Diet-Sequences to Subjects

E. WORKING MODEL USED FOR POWER ANALYSIS

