The a priori model for power analysis, planning, and for ultimately testing the primary hypotheses specifies a fairly simple linear covariance structure; namely, a three-parameter components-of-variance structure. This model is a special case of the general linear mixed model. The usual interpretation of this structure is that the underlying process involves additive errors. In other words, total variance is the sum of the components of variance. We anticipate that this model is approximately correct in spite of some sources of variation that may be multiplicative in nature. It should be noted that the assumptions made are pivotal for many of the conclusions about statistical power of test procedures that will be used. The following notation suppresses the details of the fixed effects of interest in order to focus on the details of the covariance structure.

$\mathbf{Y}_{i,d,p,t}$		< the assay value for the i^{th} subject at time t when fed diet d in period p.
	$= \alpha_{\rm d} + \pi_{\rm p}$	< the population mean for diet d in period p. These fixed-effect are of primary interest.
	+ S _i	< "subject random effect". This is the amount by which subject i consistently differs from the population mean averaging over all possible diets.
	+ Z _{i,p}	< "subject*period random effect". This term has an alias, "subject*diet random effect (Z _{i,d})", in this model because no subject can be fed to two different diets in a single period.
	+ $e_{i,d,p,t}$	< a residual error term. This quantity is different for each combination of i , d , p , and t . This catch-all term includes day-to-day variation, measurement error, etc., collectively called "within-subject" or "intra-subject" variation.

Total variance is constant and is the sum of three component variances:

 $V[Y_{i,d,p,t}] < -- \text{ total variance} \\ = V[S_i] < -- \text{ subject variance} \\ + V[Z_{i,p}] < -- \text{ subject*period variance} \\ + V[e_{i,d,p,t}] < -- \text{ residual variance} \end{cases}$

In comparing diets D and F, simple differences such as $(Y_{i,D,p,t}-Y_{i,F,p',t})$ have variance that increases with both residual variance and subject*period variance:

$$V[(Y_{i,D,p,t}-Y_{i,F,p',t})] = 2^{*}(V[Z_{i,p}] + V[e_{i,d,p,t}])$$

Serial correlation within a period is greater than serial correlation between periods:

Corr[$Y_{i,D,p,1}$, $Y_{i,D,p,2}$] = ($V[S_i] + V[Z_{i,p}]$) / $V[Y_{i,d,p,l}]$ Corr[$Y_{i,D,p,t}$, $Y_{i,E,p',t}$] = ($V[S_i]$) / $V[Y_{i,d,p,t}]$

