F. WORKING MODEL PARAMETERS

Collaborative "Period 1" data from DELTA protocol 1 and previous data sets provided by the Columbia and Penn State Field Centers have been analyzed to obtain estimates of the covariance parameters of the working model. The DELTA data provided estimates of the sum ($V[S_i] + V[Z_{i,p}]$) for seven responses (TC, HDL, LDL, Trig, Fibrinogen, Factor VII, PAI-1). Columbia data (TC, HDL, Trig) provided estimates of the ratio of correlation coefficients

Corr[$Y_{i,D,p,1}, Y_{i,E,p',1}$]	V [S _i]	= .75	.	17-
$Corr[Y_{i,D,p,1}, Y_{i,D,p,2}]$	$V[S_i] + V[Z_{i,p}]$			/

This ratio is the proportion of subject-related variance accounted for by the "subject" random effect. In the data from Columbia the proportion ranged from 73% to 93%. The data from Penn State also provided evidence that this ratio varies from one analyte to another but indicated a different rank order for the analytes. This collective information was used in conjunction with the DELTA data to obtain approximate estimates of $V[S_i]$ for the seven analytes. In particular, all power computations reported here assume an approximate value of 85% for the ratio of correlation coefficients. All three data sets were used to assess evidence of constancy of variance and constancy of the two correlation coefficients. Several alternative covariance structures for the Columbia data were considered and were rejected using likelihood ratio tests. These included (1) the "compound symmetry" structure, (2) first-order autoregressive structure, and (3) power structures for spacial/temporal data.

All power analysis results reported here were based on the assumption that N=100 subjects will complete the study, 25 from each of the four Centers, as shown in Table 1. We assume that diet sequences will be randomly assigned to subjects as indicated in Table 2. We assume that the actual values of diet differences (and all other model parameters) are fixed and unknown for the study population.

	Ехри	ressed as V	ariance	Expressed as i	Standard Deviation
	Variance Estimate	Standard Error of Estimate	95% Confidence Interval for Variance Est.	Square-Root of Estimate	95% Confidence Interval for Std. Dev. Est.
Cholesterol					· •• •• •• •• ••
Inter-Subject	727.23	103.54	[524.28, 930.18]	26.97	[22.90, 30.50]
Intra-Subject	106.02	7.94	[90.44, 121.60]	10.30	[9.51, 11.03]
IDL.					
Inter-Subject	113.85	15.94	[82.61, 145.10]	10.67	[9.09, 12.05]
Intra-Subject	8.92	0.66	[7.61, 10.24]	2.99	[2.76, 3.20]

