LDL			_		
Inter-Subject	663.24	94.05		25.75	[21.88, 29.11]
Intra-Subject	85.41	6.40	[72.86, 97.96]	9.24	[8.54, 9.90]
Triglyceride					
Inter-Subject	1336.22	192.41	[959.10, 1713.3]	36.55	[30.97, 41.39]
Intra-Subject	267.07	20.01	[227.84, 306.30]	16.34	[15.09, 17.50]
Fibrinogen .					
Inter-Subject	2353.25	343.86	[1679.29,3027.21]	48.51	[40.98, 55.02]
Intra-Subject	611.29	45.63	[521.84, 700.74]	24.72	[22.84, 26.47]
Factor VII					
Inter-Subject	178.82	25.97	[127.92, 229.73]	13.37	[11.31, 15.16]
Intra-Subject	40.61	3.05	[34.64, 46.59]	6.37	[5.89, 6.83]
PAI-1					
Inter-Subject	57.63	8.72	[40.52, 74.73]	7.59	[6.37, 8.64]
Intra-Subject	22.34	1.67	[19.06, 25.62]	4.73	[4.37, 5.06]

	Table 3
Estimation	of Variance Components
Based on Data	from Period 1 of Protocol 1

NOTE: These estimates were obtained by fitting components-of-variance models to the preliminary data from period 1 of protocol 1. Each such model included fixed effects for Diet, Gender-Group, Diet*Gender-Group, and Center. Under the assumptions of the working model described above, the "Intra-Subject Variances" given in this table are estimates of the sum of subject-related components ($V[S_i] + V[Z_{i,p}]$). The "Inter-Subject Variances" are estimates of the "residual variance" defined in the working model.

G. POWER ANALYSIS COMPUTATIONS AND RESULTS

All power analysis results are based on the following assumptions: (1) the hypothesis test is performed at the 0.01 level of significance, (2) the sample size is N=100, (3) the sample is distributed as shown in Tables 1 and 2, (4) the endpoint is an average of three weekly blood draws ("REPS=3" in the figures), (5) variances are as shown in Table 3, (6) the variancecovariance structure for the repeated measurements has the covariance structure previously described, (7) a correlation ratio of 85% (see above discussion), (8) fixed effects for gender, race, center, age, period, diet, and gender*diet interaction, (9) no carryover effects. Computations were made using probability functions available in the IML Procedure published by SAS Institute, Cary, NC.

Figures 1-8 present a summary of the results in terms of "minimum detectable differences" when power is held fixed at 90%. This concept is illustrated in Fig. 1 (TC).

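### The a priori model has one period effect for all centers; if periods shift differently by center, adding center*period would protect power at almost no cost

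*Protocol*

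**What the plan says.** Chapter 4 E describes the a priori "model for power analysis, planning, and for ultimately testing the primary hypotheses". Its mean has two parts, a diet effect and a period effect, and the period effect has no center index. The random part has a subject effect, a subject*period effect (aliased with subject*diet) and a residual.

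Chapter 4 G gives the only itemized list of fixed effects: "8) fixed effects for gender, race, center, age, period, diet, and gender*diet interaction". No center*period term appears there or elsewhere in the protocol.

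On allocation, Chapter 4 D says: "Highest priority will be given to balance within field centers". The stated reason is clear interpretation of ancillary studies. Chapter 5 A repeats that balance is sought at the level of the field center, and by gender and race.

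On time effects, Chapter 4 B notes that "period effects are frequently noted in dietary feeding studies" and expects to see them in this trial.

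**The concern.** In a three-period crossover the diet comparison is made within subjects. Gender, race, center and age do not change within a subject, so as main effects they neither adjust nor sharpen that comparison. The within-subject terms in the list are diet, gender*diet and the single common period effect.

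Subjects at one center share a kitchen, local food purchases (Chapter 8 A) and local collection staff in each period. A shift in the outcome that is specific to one center in one period would affect all 25 of them alike. Because diets are balanced within center and period, such a shift nearly cancels from the diet estimate. The listed model cannot assign it to a block, however, so it goes into the subject*period error. The trial would then have the blocking but not its benefit: a reported standard error wider than the estimate's true variability, an actual test size below 0.01, and power below the planned 90%.

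**Working it through.** **Inputs**
- Test level: "the hypothesis test is performed at the 0.01 level of significance" (Chapter 4 G). Sidedness is not stated; two-sided is assumed. Power 90%.
- "N=100 subjects will complete the study, 25 from each of the four Centers" (Chapter 4 F).
- "the endpoint is an average of three weekly blood draws" (Chapter 4 G).
- Total cholesterol, Table 3: 727.23 and 106.02; correlation ratio 0.85. Here 727.23 is taken as V[S]+V[Z] and 106.02 as the residual. The note under Table 3 attaches these meanings the other way round, but that reading gives a minimum detectable difference (MDD) of about 9.6 mg/dl, not the stated 7.2.
- Gender groups, Table 1: 23, 21 and 56. Their placement by center is taken from Table 1.
- SD of the center-by-period shift: **not in the documents; an assumption**, shown as a range.

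**Step 1. Reproduce the protocol's figure (7.2 mg/dl, Chapter 4 G)**
- V[Z] = 0.15 × 727.23 = 109.08.
- Variance of a subject's period mean: 109.08 + 106.02/3 = 144.42.
- With gender*diet in the model and equal weight on the three groups: w = (1/23 + 1/21 + 1/56)/9 = 0.01211.
- SE = √(2 × 144.42 × 0.01211) = 1.87.
- MDD = (2.576 + 1.282) × 1.87 = 7.21 mg/dl. This agrees.
- The exact within-subject design matrix from Table 2, with a t reference, gives SE 1.876, 192 error df and MDD 7.30.

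**Step 2. Check the balance**

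At center C, sequence DEF has 5 subjects and the others 4. In period 1, D has 5 + 4 = 9, E has 8 and F has 8. The other 11 center-by-period cells also hold 8, 8 and 9. The center main effect has a within-subject column of exactly zero.

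**Step 3. Cost of the term when there is no shift**

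Adding center*period: SE 1.876 → 1.878, error df 192 → 186, MDD 7.30 → 7.31 mg/dl.

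**Step 4. Effect of a shift with SD σ when the term is absent**

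The shifts add 25 × (4−1) × (3−1) × σ² = 150σ² to the expected error sum of squares, so the error variance becomes about 144.42 + (150/192)σ².
- σ = 3: 151.5, SE 1.876 × √(151.5/144.42) = 1.92
- σ = 5: 164.0, SE 2.00
- σ = 8: 194.4, SE 2.18

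Simulation (10,000 trials per row, Table 2 allocation, gender*diet in the model, true difference 7.30 mg/dl) agrees:

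| Shift SD (mg/dl) | SE reported, no term | True SD of estimate | Size, no term | Power, no term | Power, with term |
|---|---|---|---|---|---|
| 0 | 1.88 | 1.88 | 0.0105 | 90% | 90% |
| 3 | 1.92 | 1.88 | 0.0087 | 89% | 90% |
| 5 | 2.00 | 1.88 | 0.0063 | 86% | 90% |
| 8 | 2.17 | 1.89 | 0.0046 | 80% | 90% |

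With the term, the reported SE stays at 1.88 and the size is about 0.01 in every row.

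**Step 5. Scale of the assumed shifts**

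Against V[Z] = 109.08, the shift variances are 9/109.08 = 8%, 25/109.08 = 23% and 64/109.08 = 59%. An SD of 8 is therefore large.

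**The case against.** **The list in section G is a set of power assumptions, not an analysis specification.** Section E says its notation leaves out detail on the fixed effects, section B leaves fine points to writing groups, and it promises to examine sensitivity to modeling assumptions. This has weight: reading the list as the test model is an inference. It is a reasonable one, because section E uses one a priori model for both purposes and writes its period effect without a center index. A sensitivity check would not change the primary test.

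**No evidence of center-specific shifts is offered.** The break dates in Chapter 5 A are common to all centers, so shared holiday effects go into the common period term. Chapter 9 V has all of a subject's samples for an analyte assayed in one run, which removes run-to-run drift. Fats, oils, most beef and cheese are bought centrally (Chapter 8 A). This stands and limits the likely size. It does not exclude a shift: some food is local, and Chapter 8 B itself plans to study variation between centers and over time. Nor could the Table 3 variances reveal one, since they come from a single period with center fitted.

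**The loss lies within the planned margin.** At SD 5 and 8 the error variance rises by about 13% and 34% (2.00²/1.876² and 2.17²/1.876²), inside the 50% pessimistic curve of section G. True, but this part of the loss is avoidable.

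**The same logic would support gender*period**, since Chapter 5 A also balances on gender. That is fair. Center has the better claim because its subjects share food, staff and facilities, and because section D ranks it first.

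A reader might infer that the planned standard errors are simply too wide. The documents do not support that: without center-specific shifts they are correct. Nor do they support a reading of bias or excess false positives, because the error is conservative. A reader might also expect dropout to spoil the cancellation. That is possible in principle, but all calculations here assume 100 completers and no size can be given.

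**Conclusion.** The point holds conditionally. The a priori model as written does not use the center-by-period blocks that the allocation balances. If period effects differ between centers, the reported standard error for total cholesterol is about 2%, 6% and 16% too wide at shift SDs of 3, 5 and 8 mg/dl. Power is then about 1, 4 and 10 points below the planned 90%. If they do not differ, the planned analysis is correct and the extra term changes nothing of note.

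The conclusion rests on three assumptions: shift sizes that the documents do not supply, a two-sided test, and the section G list being the model for the primary tests. The balance in Table 2 and the near-zero cost of the term do not depend on the shift size. The recommendation is therefore sound as inexpensive insurance, not as repair of an invalid test.

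**What to change.** In Chapter 4 E, give the period effect a center index. In Chapter 4 G, add center*period (equivalently, period within center) to the fixed effects for the primary diet contrasts, and state that the power model and the test model share this term. Describe it as protection of power under the within-center allocation of section D.

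The cost is one model term, with no change to sample size, allocation, visits or assays. The degrees of freedom and MDD cost are those in Step 3 of the working, so the 7.2 mg/dl planning figure need not be revised for this reason.
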